8.3. Criteria for Termination of Trial Based on Statistics and Justification

The interim analysis and its corresponding early termination criteria are not pre-established in this trial, so this section is not applicable. All statistical analyses are conducted after the completion of data collection, cleaning and final locking.

8.4. Data Statistical Method, with the Handling Method of Missing, Unused and Wrong Data (Including Discontinuation and Withdrawal) and Unreasonable Data

Missing data handling method: The missing data will be processed according to the division of the data set; primary efficacy data will be imputed with the use of the WOCF (Worst Observation Carry Forward).

Wrong data handling method: In the process of data management, the quality management will be performed for the data in the database, wrong data found will be questioned in the form of Query to investigators, and the wrong data will be adjusted according to the written reply of investigators until all wrong data is corrected before locking the database.

Unreasonable data handling method: In the process of data management, the data in the database will be checked logically, unreasonable data found will be questioned in the form of Query to investigators, and the unreasonable data will be adjusted according to the written reply of investigators until all unreasonable data is solved before locking the database.

8.5. Procedures for Reporting Deviation from Original Statistical Plan

The statistical analysis plan needs to be confirmed by the sponsor and the principal investigator and finalized before the database is locked. Prior to finalization, the initial analysis plan should be modified according to the actual conditions in the trial process. In principle, the main analysis principles, methods and analysis sets should not be modified, and all the modifications will be recorded.

8.6. Selection Criteria for Subjects Included in the Analysis and

Justification

Statistical analysis will be carried out on the basis of the following analysis populations. The analysis populations will be clearly defined before the start of statistical analysis. And the analysis populations in this study include:

Full Analysis Set (FAS): The set of subjects determined following the intent-to-treat (ITT) principle refers to the data set constituted by all subjects who participate in the randomized study and receive the investigational product. For patients in whom the primary effectiveness endpoint is not observed, missing data are proposed to be carried forward using the WOCF (Worst Observation Carry Forward).

Per-Protocol Set (PPS): refers to the subgroups of treatment population where the study has been completed with the major protocol violations excluded (which means that the subjects violate the inclusion criteria or exclusion criteria, etc.).

Safety Set (SS): refers to the set of all subjects who receive the investigational device and complete safety evaluation at least once.

8.7. Exclusion of Special Data During Hypothesis Test and Justification (if applicable)

N/A

9. Data Management

The Electronic Data Capture (EDC) system is used to collect the trial data. The EDC system has been strictly tested and fully complies with the requirements of Good Clinical Practice for Medical Devices and Technical Guidance for Data Management in Clinical Trials. Before the system is formally launched, the relevant users need to be trained and assessed to ensure that the system meets the trial requirements. After the official launch, relevant personnel will be provided with the account and password. The account is bound with the role and authority of the user who is required to properly keep and not to disclose the account information to others or exercise corresponding rights on behalf of others.

9.1. Data Collection

The EDC directly transmits data from the client to the server through the Internet. Investigators can directly enter the source data into the EDC system to complete data collection. Investigators should be responsible for the quality of the entered data and ensure the authenticity and integrity of the data. The EDC system provides an interface printing function that allows the investigator to print the electronic case report form as required.

9.2. Data Verification and Modification

The EDC system provides on-line and off-line verification methods. When

investigators have entered abnormal data, the EDC system will issue real-time warnings to remind them to check; and the data administrator performs logical check on the data stored in the server and issues the wrong data through EDC in the form of manual query. Investigators need to answer all published questions. The CRA needs to periodically remind and assist the investigators in answering queries to ensure that each query is handled correctly. The system will record all queries and answers thereto.

9.3. External Data Management

External data in the study, such as device parameters and review results of central interpretation room, require pre-defined transmission mode, format requirements, transmission frequency and encryption and must meet the requirements for later data management and statistical analysis. For data management, the completeness, consistency and accuracy of external data should be verified, and in case of any problematic data, the external data output party should explain or modify it to ensure that it can be combined with the ECRF database.

9.4. Database Locking

When all data entry is completed and submitted, and all queries are answered, the system enters a soft locking status. The statistician will generate a masked review report based on the database. If it is confirmed that the data would not be modified, the sponsor, the person in charge of data administration and the person in charge of statistics will sign the database locking form, and the data administrator would complete the database locking operation according to the form. The locked database cannot be modified again. If there is any wrong data that affects the primary effectiveness endpoint or safety indicators, the sponsor, the person in charge of data management and the person responsible for statistics will confirm the unlocking for modification and sign the database unlocking form, and the data administrator will modify the wrong data according to the unlocking reason and carry out quality control. The sponsor, the person in charge of data administration and the person in charge of statistics will sign the database locking form again once the error had been corrected.

10. Feasibility Analysis

10.1. Possibility Analysis on Success

According to the clinical trial and clinical application of similar products, the application of mechanical revascularization device for treatment of acute ischemic stroke is safe and effective, because of its navigation and rapid recanalization advantages, and freedom from risk of long-term complications. In the Chinese Guidelines for the Endovascular Treatment of Acute Ischemic Stroke (2018), mechanical thrombectomy for acute anterior circulation great-vessel occlusive stroke within 6h of onset is classified into Class I recommendation

(Level A evidence). According to the results of DEFUSE-3 and DAWN studies, patients with onset at 6-16h and 16-24h meet the corresponding inclusion and exclusion criteria and are classified into Class I recommendation (Level A evidence) and Class IIa recommendation (Level B evidence), respectively. According to the 2018 AHA/ASA, mechanical thrombectomy is recommended as Class I recommendation (Level A evidence) for acute ischemic stroke patients within 6-16h from the last time being normal and target lesions in the anterior circulation great vessels if the enrollment meets the DOWM or DEFUSE-3 criteria. Mechanical thrombectomy is recommended as Class IIa recommendation (Level B evidence) in acute ischemic stroke patients within 6-24h from the last time being normal and target lesions in the anterior circulation great vessels if the enrollment meets the DOWM or DEFUSE-3 criteria.

The design of Ghunter Revascularization Device of Sinomed Neurovita Technology Inc. is optimized on the basis of similar products that have been marketed, and there is no difference in their main technical indicators. Before conducting the clinical trial, animal experiments have been performed to verify that Sinomed Neurovita Ghunter Revascularization Device is not inferior to the marketed product in terms of effectiveness and safety.

The clinical sites participating in this study are equipped with complete instruments and equipment and are the hospitals with rich clinical experience; the physicians participating in this study have rich experience in using mechanical intracorporeal thrombectomy stents.

10.2. Possibility Analysis on Failure

The main reasons for failure or poor results may be related to the following factors: 1) The product is seen very special device defects. 2) Too many subjects dropped out due to the development of SAEs. 3) The training for the personnel of the study site is not in place, and the use of the device is not skilled, with the result that the effectiveness of the product fails to meet the requirements.

In addition to the above reasons, there are other unpredictable risks that may exist in this study, leading to its failure. But the risk may be minimized by adherence to this protocol, treatment in the prescribed study sites, compliance with the inclusion/exclusion criteria of the subjects, and close monitoring of the physical condition of the subjects during the treatment or follow-up period.

11. Quality Control of Clinical Trial

11.1. Monitoring of Clinical Trial

During the clinical trial, the CRA will conduct regular monitoring visits at the study site according to the monitoring plan, to ensure that all the contents in the study protocol are strictly observed, and will check the raw data to ensure that the filled contents of EDC are true, complete and correct.

11.2. Filling of Case Report Form

Permissible users perform data entry to ensure that the raw data are consistent with EDC data.

11.3. Retention of Raw Data

The raw data of this trial include the signed ICF, release records of test products, relevant laboratory test report, case records and other related records, which should be retained at the clinical study site of the hospital where the study site is located. All raw data and printed CRF should be retained for 10 years after the end of clinical trial.

12. Ethical Issues and Informed Consent in Clinical Trial

12.1. Ethical Considerations

Before the clinical trial, the investigators need to submit the clinical trial protocol, ICF and other related documents to the Medical Ethics Committee of hospitals where the study sites are located. The clinical trial will be started only after obtaining the approval of the Ethics Committee. Any amendment to the study protocol must be approved by the Ethics Committee before it can be implemented. SAEs during the clinical trial shall be submitted to the Ethics Committee in writing timely.

12.2. Approval of Trial Protocol

The approval of the clinical trial protocol is performed by the Ethics Committee, and the clinical trial can be performed only after obtaining the final ethical approval.

12.3. Informed Consent Process and Contents of Informed Consent Form

The investigators must specify to the subjects or their guardians, prior to their enrollment, the details of this clinical trial, including the contents and purpose of the trial, intended efficacy, possible adverse events and countermeasures. The subjects can only be enrolled when they have fully understood this trial and signed the ICF.

For incompetent subjects, if the Ethics Committee agrees in principle and the investigators believe that it is in their own interests for the subjects to participate in the clinical trial, they may also enter the clinical trial, but their guardians should sign and date before the trial. Although acute ischemic stroke patients may not be clinically comatose, their cognitive ability and hand function are affected, and such subjects should be signed and dated by their guardians before the trial.

When the subjects or their guardians have no reading ability, a witness shall be present in the informed process. After the detailed explanation of the ICF, the

witness's reading of the ICF shall be consistent with the oral informed content. After the subjects or their guardians show verbal consent, the witness shall sign and date the ICF and the signatures of the witness and the investigator shall be on the same day.

13. Provisions for AE and Device Defect Reporting

13.1. AE

13.1.1. Definition of AE

An AE is defined as any untoward medical occurrence after treatment with the investigational product, regardless of its relationship to the investigational medical device. This includes the events related to the followings:

- All events related to the investigational or control device.
- All events related to the study process (all processes in the clinical study plan).
- Other adverse events.

13.1.2. Determination of AE Severity

The process, degree, handling and outcome of the adverse events should be observed in detail and be filled in the Adverse Event Report Form. According to the following criteria, the severity of adverse events can be divided into mild (inquired), moderate (active narration, but able to endure) and severe (objective manifestation, unendurable).

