6.1.5. Subject Enrollment

6.1.5.1. Inclusion Criteria

General inclusion criteria:

- 1) ≥ 18 years old;
- 2) NIHSS ≥ 6 at randomization;
- 3) Pre-onset mRS < 2;
- 4) Acute ischemic stroke was diagnosed;
- 5) Within 24h from the stroke onset to the completion of femoral artery puncture (regardless of whether intravenous thrombolysis has been performed); the time point of stroke onset is defined as the time point at which the patient is last known to be normal;
- 6) The subject (or his/her guardian) agrees to participate in this study and signs

the informed consent form (ICF).

Angiographic inclusion criteria:

- 1) Cerebral CT or MR should be performed when the time from the stroke onset to the completion of femoral artery puncture of a patient is ≤ 6 h;
- 2) Cerebral CT or MR should be performed when the time from the stroke onset to the completion of femoral artery puncture of a patient is 6 (exclusive)-24h (inclusive), and his/her ASPECTS score should be ≥ 6 . (If immediate CT perfusion imaging or MR perfusion imaging is feasible, it is recommended to perform CTP or MRP simultaneously to assist in the assessment of the infarct core, and his/her ASPECTS score should also be ≥ 6);
- 3) DSA angiography shows acute occlusion of large intracranial arteries, including intracranial internal carotid artery (C4-C7), middle cerebral artery (M1/M2), basilar artery and intracranial vertebral artery (V4).

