13.1.3. Recording of AE

AEs after treatment with the investigational product must be recorded truthfully in the Adverse Event Form. Record the duration of adverse events (that is, from start to end), severity, and correlation with the clinical study of adverse events as well as the corresponding treatment and other management measures. Follow-up shall be made to the end of the trial or the outcome of adverse events.

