13.3. SAE

The SAE refers to the event that causes death or serious deterioration of health in the process of clinical trial, including:

- Fatal disease or injury;
- Permanent impairment of a body structure or a body function;
- Requiring in-patient hospitalization or prolongation of existing hospitalization;
- Requiring medical treatment or surgical intervention so as to avoid permanent impairment of the body structure or body function;
- Leading to a fetal distress, fetal death or a congenital abnormality;
- Congenital defect, etc.

Hospitalization or prolongation of hospitalization cannot be considered an SAE if at least one of the following exceptions is met:

- 1) Pre-planned hospitalizations (e.g., scheduled elective or scheduled operations or examinations prior to study start)
- 2) Hospitalization not related to an AE (e.g., community hospitalization for short-term or long-term care purposes)
- 3) Measures such as tracheal intubation or tracheotomy to help stroke patients breathe better with sputum
- 4) Not symptomatic intracranial hemorrhage as judged by the investigators

Note: Symptomatic intracranial hemorrhage refers to intracranial hemorrhage (parenchymal hematoma, subarachnoid hemorrhage, ventricular hemorrhage) accompanied by neurological deterioration (NIHSS score increases by ≥ 4 compared with that preoperatively)

However, any interventional therapy performed during hospitalization may meet the criteria for a "significant medical event" and may be reported as a SAE based on clinical judgment. In addition, if local regulatory authorities specifically require stricter definitions, local regulations shall prevail.

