6.7.3. Adverse Events

Table35 Summary of Adverse Events

Item	Experimental Group (n=)		Control Group (n=)		Total (n=)	
	Number of Occurrence	Incidence Rate (%)	Number of Occurrence	Incidence Rate (%)	Number of Occurrence	Incidence Rate (%)
Adverse Event						
Mild adverse events						
Moderate adverse events						
Severe adverse events						
Adverse events related to the investigational device						
Adverse events leading to subject withdrawal from the trial						
Adverse events resulting in death						

Note: Definition of trial device-related adverse events: Adverse events classified as "definitely related," "probably related," "possibly related," or "unclassifiable" to the trial device.

Table36 Summary of Serious Adverse Events

Item	Treatment Group (n=)			Control group (n=)			Total (n=)		
	Occurrence	Number of Subjects	Incidence Rate (%)	Occurrence	Number of Cases	Incidence Rate (%)	Number of cases	Incidence Rate (%)	P value
Serious Adverse Events related to the investigational device									
Serious adverse events resulting in death									

Note: Definition of serious adverse events related to the investigational device: Serious adverse events determined to be "definitely related," "probably related," "possibly related," or "unclassifiable" to the investigational device.

Table37 Event Coding

Item	Experimental Group (n=)			Control Group (n=)			Total (n=)		
	Occurrence	Number of Subjects	Incidence Rate (%)	Occurrence	Number of Cases	Incidence Rate (%)	Number of cases	Incidence Rate (%)	P value
Adverse Event									
SOC1									
PT1									
PT2									
.....									
SOC2									
.....									

Table38 Serious Adverse Event Codes

Item	Experimental Group (n=)			Control Group (n=)			Total (n=)		
	Occurrence	Number of Subjects	Incidence Rate (%)	Occurrence	Number of Cases	Incidence Rate (%)	Number of cases	Incidence Rate (%)	P value
Serious Adverse Events									
SOC1									
PT1									
PT2									

	Experimental Group (n=)	Control Group (n=)	Total (n=)	
Item	Number of Occurrence Subjects	Incidence Rate (%)	Number of Cases	Incidence Rate (%)
.....				
SOC2				
.....				

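### The AE severity scale grades how an event was reported and tolerated rather than its clinical impact, so it gives no determinate grade for patients who cannot report or for silent imaging and laboratory findings

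*Protocol*

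**What the plan says.** Protocol 13.1.2 asks that the course, degree, management and outcome of each event be observed and recorded, and then states that "the severity of adverse events can be divided into" three grades: "mild (inquired), moderate (active narration, but able to endure) and severe (objective manifestation, unendurable". Protocol 13.1.3 requires recording of "severity, and correlation with the clinical study of adverse events", along with duration and treatment.

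The grade is then reported. Protocol 7.1.2.5 describes the degree of AEs in each group, and SAP 5.5 describes their severity. SAP 6.7.3, Table 35, has separate rows by arm for mild, moderate and "Severe adverse events". The SAP does not redefine the grades.

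On the population, Protocol 6.1.5.1 requires "NIHSS ≥ 6 at randomization" with no upper limit, and admits basilar and intracranial vertebral occlusions. Protocol 12.3 says of these patients: "Although acute ischemic stroke patients may not be clinically comatose, their cognitive ability and hand function are affected", and has guardians sign for them.

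**The concern.** A severity grade should say how much an event affected the patient. Here, *mild* means that someone had to ask, *moderate* means that the patient spoke up and could bear it, and *severe* combines an objective sign with being unbearable. None of the three mentions function, treatment or danger to life.

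That is a poor measure in any trial. In a large-vessel stroke trial, some patients cannot answer, volunteer a complaint or say what they can tolerate, and several relevant events are found by a scan or a blood test. Table 35 is the by-arm summary of how bad the AEs were. If the same event can receive different grades at two sites that both follow the protocol, a reader cannot interpret that part of the table.

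**Working it through.** There is no plan figure to reproduce, so the check sets the scale beside the patients and events that the protocol expects.

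**1. Patients who cannot report are foreseen.** Appendix 5 has scoring rules for aphasic and stuporous patients (item 1b), for coma and for mute or globally aphasic patients (item 9), and for intubated patients (item 10). Protocol 13.3 mentions intubation and tracheotomy. General exclusion 11 covers disorders that could disturb neurological assessment, but it does not name aphasia or coma from the index stroke. Protocol 13.1.2 has no proxy, guardian or clinician rule for such patients.

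**2. Silent findings are foreseen.** The AE definition in 13.1.1 does not require symptoms. Visit 3 imaging records haemorrhage and new infarction, and laboratory tests are repeated after the procedure.

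**3. Apply the scale.** The text does not say whether the two parts of the severe grade are alternatives or must both be met, so both readings are shown.

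| Case | Mild | Moderate | Severe, objective sign suffices | Severe, both parts needed |
|---|---|---|---|---|
| Aphasic patient, visible event needing non-urgent treatment | Cannot answer | Cannot narrate | Severe | No grade: tolerance unknown |
| Silent haemorrhage on the 24 h scan | Not found by asking | Not narrated | Severe | No grade: nothing to endure |
| Laboratory abnormality, no symptoms | Not found by asking | Not narrated | Severe, if a result counts as an objective sign | No grade |
| Fatal event in a comatose patient | Cannot answer | Cannot narrate | Severe | No grade: tolerance unknown |

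On the first reading, a trivial sign and a fatal event share the top grade. On the second, neither has a grade. Even in a patient who can speak, an event that emerges only on questioning meets the definition of mild, whatever treatment it needs.

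**4. Trace where the grade goes.** It feeds the descriptions in Protocol 7.1.2.5 and SAP 5.5, and three rows of Table 35. The safety endpoints in Protocol 6.1.7.1 are symptomatic intracranial haemorrhage, mortality, SAE, AE and device defects, and none is defined by the grade. SAE criteria in 13.3 are outcome-based. The pass rule in 8.2 does not mention grades.

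**5. Is there a size?** The share of AEs that are moderate but occur in patients who cannot narrate would be (share unable to narrate) × (share of AEs truly moderate). The documents give neither input. Assumed ranges of 30–60% and 30–50% give 0.30 × 0.30 = 9% to 0.60 × 0.50 = 30%, but that range only restates the assumptions. It also takes the two shares as independent, and takes the inability to report as lasting for as long as AEs are collected, which is to day 90. It is not an estimate for this trial.

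**The case against.** The strongest reply is that little is lost, and much of it stands. Deaths have their own row in Table 35 and their own Table 34. Serious events are summarised in Table 36. Symptomatic haemorrhage rests on imaging plus an NIHSS rise, with the imaging read centrally. Laboratory changes are cross-tabulated by clinical significance in Tables 39–49. The severity wording is permissive, and an objective sign needs no speech, so it would go too far to say that the scale cannot grade these patients at all.

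The cover is not complete. Under Protocol 13.3, hospitalization or its prolongation is not an SAE in cases listed as "Not symptomatic intracranial hemorrhage as judged by the investigators", or for intubation or tracheotomy. That exception says nothing about AE grading. But where it applies and no other SAE criterion is met, the event remains an ordinary AE, and the 13.1.2 grade is its only formal severity measure.

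A reader might also infer that the counts by arm are wrong or biased towards one device. The documents do not support that. Table 35 is an empty shell. Allocation is randomized 1:1 and both arms use one scale, so patients unable to report are balanced in expectation. Investigators know the device and no masked AE grading is described, which leaves room for differential grading but does not show it. Nor does NIHSS ≥ 6 by itself mean that a patient cannot speak.

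**Conclusion.** The point holds as a defect of measurement. The only severity scale in the plan records reporting and tolerance in place of clinical impact, and it gives no valid or determinate grade for patients who cannot report or for silent imaging and laboratory findings. This is a stated rule that misgrades when followed, not merely a missing detail.

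The consequence is limited to descriptive safety reporting: the three severity rows of Table 35 and the accompanying text would be unreliable. A reader might take the safety condition in Protocol 8.2 as tying this to trial success. That condition is a qualitative judgement and does not cite the grades, so no such link is established.

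The conclusion assumes that sites apply 13.1.2 as written and that no other grading guidance exists outside the two documents. It does not depend on any particular share of non-communicating patients.

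**What to change.** In Protocol 13.1.2, define mild, moderate and severe by observable clinical impact: effect on function, need for treatment or urgent intervention, and threat to life or death. State that grading does not require the patient's own report, and that imaging and laboratory findings are graded on the same basis. Refer to these definitions in SAP 5.5 and in a note to Table 35.

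Where feasible before database lock, have the existing investigators regrade AEs already entered, using the recorded management and outcome and without reference to arm. Protocols 13.1.2 and 13.1.3 already require that information, and the masked review in 9.4 is a natural point by which to finish.

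Cost: a protocol amendment with Ethics Committee approval before implementation (Protocol 12.1 and section 14), revised case report form guidance, and some site time for regrading. No new visits or subjects are needed. Regrading will be only as good as the recorded narratives, and a narrative that names the device would have to be edited before it is graded.
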